3.3.1.2 Secondary Efficacy Outcome Measures

The secondary efficacy outcome measures for this study are as follows:

- *Annualized rate of decline in 6MWT distance over 52 weeks*
- *Time from randomization to first occurrence of a $\geq 10\%$ absolute decline in percentage of predicted FVC or death from any cause*
- *Annualized rate of decrease in percentage of predicted DL_{CO} over 52 weeks*
- PFS, defined as the time from study treatment randomization to the first occurrence of any of the following *disease progression or death* events:
 - Death from any cause
 - All-cause hospitalization
 - A decrease from baseline (*relative change*) of $\geq 10\%$ in FVC (mL/year)
- *Annualized rate of decrease in FVC over a 52-week period (mL/year)*
- *Annualized rate of decrease in ATAQ-IPF total score over a 52-week period (see Appendix 5 for a description of the instrument)*
- *Time from randomization to first occurrence of the SGRQ (see Appendix 5 for a description of the questionnaire) worsening (total score) as defined by reaching MID (Swigris et al. 2010): Total Score = 7 or death from any cause*

- Time from randomization to non-elective hospitalization *or death from any cause*
- Time from randomization to first event of acute IPF exacerbation *as defined below:*

IPF exacerbation is defined as an event that meets all of the following criteria as determined by the investigator:

Unexplained worsening or development of dyspnea within the previous 30 days

***And** radiologic evidence of new bilateral ground-glass abnormality or consolidation superimposed on a reticular or honeycomb background pattern that is consistent with UIP*

***And** absence of alternative causes, such as left heart failure, pulmonary embolism, pulmonary infection (on the basis of endotracheal aspirate or bronchoalveolar lavage, if available, or investigator judgment), or other events leading to acute lung injury (e.g., sepsis, aspiration, trauma, reperfusion pulmonary edema)*

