4.5.15.2 St. George's Respiratory Questionnaire

The SGRQ is a 50-item health-related quality-of-life instrument that measures health impairment (Jones et al. 1992). The SGRQ was originally developed for use in COPD and asthma populations; however, it has been used to assess health impairment in IPF populations. The questionnaire contains three domains: symptoms, activity, and impacts. Items are assessed on various response scales, including a 5-point Likert scale and True/False scale. The SGRQ has a recall specification of 4 weeks. A copy of the questionnaire is provided in [Appendix 6](#).

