6.4.2 Secondary Efficacy Endpoints

The secondary efficacy end points of this study are as follows:

- PFS, defined as the time from study treatment randomization to the first occurrence of any of the following *disease progression or death events*:

Death from any cause

All-cause hospitalization

A decrease from baseline (*relative change*) of $\geq 10\%$ in FVC (L)

- Annualized rate of *decrease* in FVC (mL/year) over 52 weeks
 - Time from randomization to first *occurrence* of a $\geq 10\%$ absolute decrease in percentage in predicted FVC or death from any cause
 - Annualized rate of *decrease* in percentage of predicted DL_{CO} over 52 weeks
 - Annualized rate of *decrease* in the ATAQ-IPF total score over 52 weeks (see [Appendix 5](#) for a description of the instrument)
 - Time from randomization to non-elective hospitalization or death from any cause
 - Annualized rate of *decrease* in the 6MWT distance over 52 weeks
 - Time from randomization to first event of acute IPF exacerbation (*defined below*)
- IPF exacerbation is defined as an event that meets all of the following criteria as determined by the investigator:

Unexplained worsening or development of dyspnea within the previous 30 days

And radiologic evidence of new bilateral ground-glass abnormality or consolidation, superimposed on a reticular or honeycomb background pattern, that is consistent with UIP

And absence of alternative causes, such as left heart failure, pulmonary embolism, pulmonary infection (on the basis of endotracheal aspirate or bronchoalveolar lavage if available or investigator judgment), or other events that lead to acute lung injury (e.g., sepsis, aspiration, trauma, reperfusion pulmonary edema)

- Time from randomization to first occurrence of SGRQ (see [Appendix 5](#) for a description of the questionnaire) worsening (total score) as defined by reaching MID ([Swigris et al. 2010](#)): Total Score =7 or death from any cause
- Time from randomization to death from any cause

All continuous endpoints will be analyzed with the use of the same methodology as the primary endpoint (see previous section) *with specifics for models and summaries specified in the SAP.*

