2.2.2 Secondary Efficacy Outcome Measures

The secondary efficacy outcome measures of this study are as follows:

- Annualized rate of decrease in 6-Minute Walk Test (6MWT) distance over 52 weeks
- Time from randomization to first occurrence of a $\geq 10\%$ absolute decrease in percentage of predicted FVC or death from any cause
- Annualized rate of decrease in percentage of predicted diffusion capacity of the lung for carbon monoxide (DL_{CO}) over 52 weeks
- PFS, defined as the time from study treatment randomization to the first occurrence of any of the following disease progression or death events:

Death from any cause

All-cause hospitalization

A decrease from baseline (relative change) of $\geq 10\%$ in FVC (L)

- Annualized rate of decrease in FVC (mL/year) over 52 weeks
- Annualized rate of change in A Tool to Assess Quality of Life in IPF (ATAQ-IPF) total score over 52 weeks (see protocol for description of the instrument)
- Time from randomization to first occurrence of St. George's Respiratory Questionnaire (SGRQ; see protocol for description of the questionnaire) worsening (total score) as defined by reaching Minimal Important Difference (MID; [Swigris et al. 2010](#))

Total Score ≥ 7 or death from any cause

- Time from randomization to non-elective hospitalization or death from any cause
- Time from randomization to first event of acute IPF exacerbation (defined below)

IPF exacerbation is defined as an event that meets all of the following criteria as determined by the investigator:

Unexplained worsening or development of dyspnea within the previous 30 days

And radiologic evidence of new bilateral ground-glass abnormality or consolidation, superimposed on a reticular or honeycomb background pattern, that is consistent with UIP

And absence of alternative causes, such as left heart failure, pulmonary embolism, pulmonary infection (on the basis of endotracheal aspirate or bronchoalveolar lavage if available, or investigator judgment), or other events leading to acute lung injury (e.g., sepsis, aspiration, trauma, reperfusion pulmonary edema)

- Time from randomization to death from any cause
- Time from randomization to Respiratory hospitalization
- Time from randomization to first occurrence of a $\geq 15\%$ absolute decrease in percentage of predicted DL_{CO} or death from any cause

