2.2.3 Exploratory Efficacy Outcome Measures

The exploratory outcome measures for this study are as follows:

- Change from baseline to Week 52 in radiographic findings on pulmonary high-resolution computed tomography (HRCT), including quantitative lung fibrosis (QLF) score (see protocol)
- Change from screening (corresponding to timing for randomization strata) in serum and plasma biomarkers (e.g., periostin and CCL18) and change from baseline in serum and plasma biomarkers (e.g., periostin, CCL18, YKL40, COMP, OPN, CCL13)
- Serum lebrikizumab concentrations during the extended treatment and the 14-week safety follow-up period
- Exposure-response relationships (to be evaluated as warranted)
- Change from baseline to Week 52 in the Borg CR10 Scale
- Change from baseline to Week 52 in the ATAQ-IPF

- Time from randomization to first occurrence of SGRQ individual domain worsening as defined by reaching MID ([Swigris et al. 2010](#)).
 - Symptom=8
 - Activity=5
 - Impact=7
 - or death from any cause
- Change from baseline to Week 52 in the SGRQ
- Annualized rate of decrease in oxygen saturation levels (SpO₂) (%) over 52 weeks

The analysis plan for the exploratory HRCT and biomarkers will be specified in a separate document.

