4.4 EFFICACY ANALYSIS

All efficacy analyses will be performed on the Randomized Population. Unless otherwise specified, data collected during the 52-week placebo-controlled period will be used, regardless of whether the patient remained on treatment or discontinued the study drug early (but remained in the study). Analyses will be performed for Cohort A and Cohort B separately. For hypothesis testing, each cohort will be considered as a separate study and no type I error control will be done across the two cohorts.

For change-from-baseline endpoints, the baseline value will be defined as the measurement at randomization (Visit 2). If the randomization value is not available, the screening (Visit 1) value can be used in its place (last measurement prior to Day 1). For each subject, relative and absolute changes from baseline will be defined as follows:

- Absolute change from baseline = (post-baseline value – baseline value)
- Relative (%) change from baseline = $100 * (\text{post-baseline value} - \text{baseline value}) / (\text{baseline value})$

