For time to first occurrence of a $\geq 10\%$ absolute decrease in percentage of predicted FVC or death from any cause, time to PFS, time to first occurrence of a $\geq 15\%$ decrease in percentage of predicted DL_{CO} or death from any cause, and time to first SGRQ Total Score ≥ 7 or death from any cause, deaths which occur within 168 days after the last clinic assessment and before the week 52 visit (and before start of open label treatment) will be counted as events. For the PFS analysis, hospitalization will be counted as events following the same rule as for death. Patients without an event will be censored at the last clinic assessment during the placebo controlled period. Any patients who undergo lung transplantation will be censored at the date of the transplant. Sensitivity analyses will be provided with lung transplant counted as an event for PFS and time from randomization to death or non-elective hospitalization from any cause. For the sensitivity analyses, only lung transplant, death, or non-elective hospitalization which occur within 168 days after the last clinic assessment and before the week 52 visit (and before start of open label treatment) will be counted as events.

Annualized Rate of Decrease Endpoints

The annualized rate of decrease in FVC (mL/year) will be analyzed and summarized with use of the same method as for the annualized rate of decrease in percentage of predicted FVC. Diffusing capacity, 6MWT distance, and the ATAQ-IPF score will also be analyzed and summarized with the same methods. For the annualized rate of decrease in FVC (mL/year) height, sex, and age will be included in the model as covariates.

Categorical summaries will be provided with categories of decrease of ≥ 50 meters or death before the visit, decrease of 50 to >0 meters, and stability or improvement of ≥ 0 meters for the 6MWT distance; summaries will be provided with categories of decrease of $> 15\%$ or death before visit, decrease of 15% to $>0\%$, stability or improvement of $\geq 0\%$ for percentage of predicted DL_{CO}.

Rules for missing ATAQ-IPF V3 and SGRQ data are described in Section 4.8.

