5. REFERENCES

- Efron B. The efficiency of Cox's likelihood function for censored data. *J Am Stat Assoc* 1977;72:557–65.
- Rubin DB. Multiple imputation in sample surveys – a phenomenological Bayesian approach to non response. Proceedings of the survey research methods section of the American statistical association, 1978:1:20-34.
- Rubin DB. Multiple imputation for nonresponse in surveys. John Wiley and Sons, New York, 1987.
- Westfall and Krishen. Optimally weighted, fixed sequence, and gatekeeping multiple testing procedures. *J Stat Plan Inference* 2001;99:25-40.

Appendix 1

Protocol Synopsis

TITLE: A PHASE II, RANDOMIZED, DOUBLE-BLIND, PLACEBO-CONTROLLED, STUDY TO ASSESS THE EFFICACY AND SAFETY OF LEBRIKIZUMAB IN PATIENTS WITH IDIOPATHIC PULMONARY FIBROSIS

PROTOCOL NUMBER: GB28547

VERSION NUMBER: 7

EUDRACT NUMBER: 2013-001163-24

IND NUMBER: 117,062

TEST PRODUCT: Lebrikizumab (RO5490255)

PHASE: II

INDICATION: Idiopathic Pulmonary Fibrosis

SPONSOR: F. Hoffmann-La Roche Ltd

Objectives

Efficacy Objectives

The primary efficacy objective for this study is to evaluate lebrikizumab compared with placebo as monotherapy or as combination therapy with pirfenidone background compared with placebo in patients with idiopathic pulmonary fibrosis (IPF), as measured by the *annualized rate of decline* in percentage of predicted forced vital capacity (FVC) *over 52 weeks*.

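### SAP 2.2.2 and 4.4.3 write the SGRQ worsening event as a total score of at least 7 instead of an increase of at least 7 points from baseline

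*Combined protocol and SAP*

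**What the plan says.** The SGRQ total-score event is a listed secondary endpoint and is described in several places.

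- **SAP 2.2.2** describes it as "worsening (total score) as defined by reaching Minimal Important Difference", citing a source for the MID. The line beneath gives the condition as a total score ≥ 7, or death.
- **SAP 4.4.3**, where deaths and censoring are handled, calls it "time to first SGRQ Total Score" ≥ 7 or death. The FVC and DLco events in the same sentence are each written as a decrease.
- **SAP 2.2.3** has the exploratory domain version, "first occurrence of SGRQ individual domain worsening as defined by reaching MID", followed by 8 for symptom, 5 for activity and 7 for impact.
- **Protocol 3.3.1.2 and 6.4.2** refer to worsening by reaching the MID and then give "Total Score =7 or death from any cause".
- **SAP 4.4** sets baseline for change-from-baseline endpoints at Visit 2, with the screening value as fallback. It does not link this to the SGRQ event.
- **SAP 1** says that its outcome measures and analyses override the protocol's.

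**The concern.** An MID is a size of change, so a threshold taken from one has to be applied to a difference from baseline. The SAP applies it to the score itself. A programmer working from SAP 4.4.3 would see an event rule with no baseline in it, beside two events that do state a direction of change.

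If the rule were coded that way, the endpoint would mostly record who entered the trial with an SGRQ total of 7 or more. Randomization should make that similar in the two arms. Those events would be tied at or before the Week 4 visit, leaving little information for the stratified log-rank test or the hazard ratio. The exploratory domain endpoints use the same methods (SAP 4.4.4) and carry the same gap.

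**Working it through.** The plan states no event rate, sample size or power for this endpoint, so there is no figure to reproduce. The check has three steps.

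**1. Level or change?** The word worsening and the MID in SAP 2.2.2 point to a change. So does the SAP's source for the threshold, whose title refers to "validity and first look at minimum important differences in IPF". The condition as written in SAP 2.2.2 and 4.4.3 is a level. The protocol does not settle it: its SGRQ bullet points to Appendix 5, which is the ATAQ-IPF (the SGRQ is Appendix 6), and the source it cites for the MID appears in its reference list as the ATAQ-IPF development paper.

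**2. What the literal rule does.** The schedules of assessments collect the SGRQ at randomization, Weeks 4, 12, 24, 36 and 52, and early termination. Assume that scores cannot be negative and that higher is worse; protocol 4.5.15.2 says only that the instrument "The SGRQ is a 50-item health-related quality-of-life instrument that measures health impairment".

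- Any rise of 7 or more ends at a score of 7 or more, so the literal rule misses no true worsening.
- It adds false events: every patient at or above 7 at baseline who stays there, and any patient who crosses 7 by a smaller rise (from 5 to 7, for example, a change of 2).

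**3. How many patients?** Every input here is an assumption: a 0–100 scale, baseline mean m from 15 to 50, SD s from 10 to 20, beta-shaped scores. With μ = m/100, v = (s/100)² and k = μ(1 − μ)/v − 1, the share at or above 7 is 1 − F(0.07), where F is the beta distribution with parameters μk and (1 − μ)k.

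Example, m = 30 and s = 20: k = 0.21/0.04 − 1 = 4.25; parameters 1.275 and 2.975; share 88.5%.

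| Assumed mean | SD 10 | SD 15 | SD 20 |
|---|---|---|---|
| 15 | 76.6% | 59.8% | 46.8% |
| 20 | 93.0% | 78.6% | 64.8% |
| 25 | 98.7% | 90.7% | 78.9% |
| 30 | 99.9% | 96.6% | 88.5% |
| 40 | 100.0% | 99.7% | 97.3% |
| 50 | 100.0% | 100.0% | 99.5% |

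For contrast, take the change rule with normally distributed change, mean worsening c and SD d. The share at one visit is 1 − Φ((7 − c)/d).

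- c = 0, d = 8: 1 − Φ(0.875) = 19.1%
- c = 0, d = 10: 1 − Φ(0.70) = 24.2%
- c = 4, d = 15: 1 − Φ(0.20) = 42.1%

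These are single-visit shares under assumed inputs; the cumulative share over all visits would be higher.

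**The case against.** The best reply is that nobody who reads the whole definition would code a level. SAP 2.2.2 says worsening and MID, the cited source is about important differences, and SAP 4.4.3 is a paragraph on deaths and censoring that names endpoints in shorthand: it also drops the word absolute from the DLco event. On this view the text needs tidying and nothing is wrong with the endpoint.

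Much of this stands. The intent is recoverable, and the shorthand in SAP 4.4.3 would be harmless if the definition elsewhere were complete. It is not: SAP 2.2.2, the defining section, itself gives the condition as a score ≥ 7, and no section ties the event to a baseline.

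A reader might also infer that the protocol's "Total Score = 7 or death from any cause", and the domain values with equals signs, require a change of exactly that size and so miss larger worsenings. The documents do not support that. The equals sign gives the value of the MID, and the condition is reaching it.

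The impact is also limited. The endpoint is not among the nine key secondary endpoints in the fixed sequence of SAP 4.4.1. SGRQ change from baseline to Week 52 is analysed separately (SAP 2.2.3 and 4.4.4), and protocol 6.4.2 plans change summaries at each assessment.

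**Conclusion.** The event is wrong as written in SAP 2.2.2 and 4.4.3 and should be corrected. That conclusion rests on the wording alone. The consequence is conditional on literal programming: patients would then be counted as worsened because of where they started. The share is roughly 89% or more at assumed baseline means of 30–50, falling to about 47% at a mean of 15 with SD 20.

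A reader might infer that nearly every patient is an event at the first assessment and that the hazard ratio is forced to 1. The documents do not support that as a statement of fact. They do not show that the rule was or will be coded literally, and they give no SGRQ range, mean or SD; at the lower assumed means the share is well short of nearly everyone. Nor do they support any wider damage: the primary analysis, the key secondary tests and type I error control do not use this endpoint.

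**What to change.** 1. In SAP 2.2.2 and 4.4.3, define the event as the first absolute increase from baseline of ≥ 7 points in SGRQ total score, or death from any cause.
2. In SAP 2.2.3, define the domain events as increases from baseline of ≥ 8 (symptom), ≥ 5 (activity) and ≥ 7 (impact) points, or death.
3. State that baseline is as in SAP 4.4: Visit 2, with screening as fallback where it was collected. The schedules collect a screening SGRQ in Cohort B but not in Cohort A.
4. State how patients with no baseline SGRQ are handled, consistently with protocol 6.4.2, which excludes patients without baseline values where a score involves change from baseline.
5. Confirm and record that the Cohort A analysis used the same change-based definition. Cohort A has already been unblinded and analysed (SAP 2.4), and the documents do not show how the event was programmed.

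Items 1 to 4 cost wording only and fit within the SAP amendment, which SAP 1 says is being made before Cohort B is unblinded. Item 5 is a check of existing programs, with a rerun of the Cohort A SGRQ event analyses if they used a level.

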4.5.17.3 Assessments at Study Completion/Early Termination Visit

The study completion visit occurs as part of the last Safety Follow-up Visit (see [Appendix 1](#), [Appendix 2](#), and [Appendix 3](#)). All patients will be monitored for safety for 18 weeks after receipt of the final dose of lebrikizumab or placebo study treatment.

Patients who choose to prematurely discontinue study drug will be encouraged to remain in the study and complete all remaining assessments. If this is not feasible, the patient should enter and complete the safety follow-up period unless consent has been withdrawn.

Patients who withdraw from the study (regardless of the reason) and refuse safety follow-up will be asked to return to the clinic within 30 days (± 7 days) after the last dose of study treatment for an early termination visit. Refer to [Appendix 1](#), [Appendix 2](#), and

[Appendix 3](#) for the schedules of assessments performed at the study completion or early termination visit.

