4.1 ANALYSIS POPULATIONS

4.1.1 Intent-to-Treat Population

The intent-to-treat (ITT) population will be comprised of all patients who were randomized in the study. All efficacy analyses will be performed on this population with patients grouped according to the treatment assignment at randomization.

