4.4.1 Type I Error Control Plan

The fixed-sequence testing procedure ([Westfall and Krishen, 2001](#)) will be used to control the overall type I error rate for statistical testing of the primary and key secondary efficacy endpoints.

Contingent upon statistical significance in the primary efficacy endpoint—annualized rate of decrease in percentage of predicted FVC over 52 weeks, the key secondary endpoints will be tested at a two-sided significance level of 5% in the order as shown below:

- Time from randomization to death from any cause
- Annualized rate of decrease in percentage of predicted DL_{CO} over 52 weeks
- Time from randomization to first respiratory-related hospitalization
- Time from randomization to first acute exacerbation or death from any cause
- Annualized rate of change in the ATAQ-IPF total score over 52 weeks
- Annualized rate of decrease in 6MWT distance over 52 weeks
- Time from randomization to first occurrence of a $\geq 15\%$ absolute decrease in percentage of predicted DL_{CO} or death from any cause
- Time from randomization to first occurrence of a $\geq 10\%$ absolute decrease in percentage of predicted FVC or death from any cause
- PFS defined as time to all-cause death, all-cause hospitalization or $\geq 10\%$ relative decrease in FVC (L), whichever occurs first

If a test is not significant at 0.05 level, then the subsequent test(s) will not be considered significant regardless of the associated p-value(s).

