4.4.3 Secondary Efficacy Endpoints

Time-to-Event Endpoints

The log rank test stratified by baseline lung function ($\text{FVC} < 50\%$ vs. 50% to 75% vs. $> 75\%$ predicted) will be used to compare the time to event endpoints between two treatment arms. The hazard ratio and its 95% CI will be estimated using a Cox regression model

stratified by baseline lung function. In fitting the Cox model, ties will be handled with the approximate likelihood method of Efron (1977). Kaplan-Meier plots will be provided.

Time-to-event will be measured in reference to the date of randomization. The primary efficacy assessments for the randomized placebo-controlled period are made on through the Week 52 visit, assessment on this day will be included for analyses of the randomized placebo-controlled period, but subsequent assessment during the open-label period or after Week 52 will be excluded. Patients are considered to be in the placebo controlled period even if they have discontinued study treatment if they would still be receiving placebo controlled study treatment had they not discontinued. For time to non-elective hospitalization or death from any cause, time to first event of acute IPF exacerbation, time from randomization to death from any cause, and time to respiratory hospitalization, patients not experiencing an event will be censored at the earlier of last known alive day, study day 368 or the last date during the placebo-controlled period.

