4.4.5 Sensitivity Analyses

The following additional sensitivity analyses will be performed:

- A. A Rank ANCOVA analysis of change from baseline to week 52 in percentage of predicted FVC stratified by baseline lung function (FVC < 50% vs. 50% to 75% vs. > 75% predicted) will be performed with death ranked as worst according to time until death (patient with the shortest survival time will be assigned the worst rank) and other missing results imputed the last observation carried forward method. These analyses will be performed as described in [Stokes et al. 2000](#).
- B. The annualized rate of decrease in *percentage of* predicted FVC over 52 weeks and the annualized rate of decrease in percentage of predicted DL_{CO} over 52 weeks will be performed using the random slope model with missing due to death imputed with the worst value observed in the study during the randomized treatment period, through week 52, among any Cohort A patient. Other missing data will be implicitly imputed by the model based on an individual's estimated rate of worsening of lung function prior to study visit discontinuation (i.e., assuming missing at random).
- C. The annualized rate of *decrease in percentage of* predicted FVC over 52 weeks will be performed using the random slope model with missing data imputed with the multiple imputation method only from placebo patients. The multiple imputation method will be implemented with the following specifications.
 1. 100 imputation datasets will be created separately from steps a and b
 - a) The MCMC method will be used for partial imputation of non-monotone missingness, only to produce a monotone missing pattern. The seed will be 5815733.
 - b) The monotone method will then be used with regression method. The baseline lung function (FVC < 50% vs. 50% to 75% vs. > 75% predicted), treatment group, and all prior visits will be included in the model to impute the following visit. The seed will be 8246205

2. The random slope analysis will be performed for each imputation dataset and the results will be combined following the methodology developed by Rubin (1978, 1987).

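### All-cause death gates eight endpoints, but some patients who leave early have no planned vital-status check at Week 52

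*Combined protocol and SAP*

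**What the plan says.** **Gate.** SAP 4.4.1 uses a fixed sequence at two-sided 5% after the primary endpoint. All-cause death is the first of nine key secondaries. Once a test misses, nothing after it can be called significant. SAP 4.1.1 defines the population: "The intent-to-treat (ITT) population will be comprised of all patients who were randomized in the study".

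**Follow-up.** Protocol 4.5.17.3 encourages patients who stop study drug to stay for all remaining assessments, then adds: "If this is not feasible, the patient should enter and complete the safety follow-up period unless consent has been withdrawn". Protocol 4.6.1.1 sets that follow-up at 18 weeks after the last dose. Protocol 4.6.1.2 asks sites to make every effort to obtain information on patients who withdraw, and rules out follow-up after consent is withdrawn. None of these sections asks for vital status at Week 52.

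**Censoring of the death endpoint.** SAP 4.4.3 names all-cause death among the endpoints covered by this rule: "patients not experiencing an event will be censored at the earlier of last known alive day, study day 368 or the last date during". That last limit is the end of the placebo-controlled period, and patients who have stopped drug are treated as still in it. The next paragraph, which opens with the FVC, PFS, DLco and SGRQ composites, says: "Any patients who undergo lung transplantation will be censored at the date of the transplant".

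**Sensitivity analyses.** SAP 4.4.3 states: "Sensitivity analyses will be provided with lung transplant counted as an event for PFS and time from randomization to death or non-elective hospitalization". Analyses A to D in SAP 4.4.5 cover only percent predicted FVC and DLco. No sensitivity analysis covers death alone.

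**The concern.** The death test decides the formal status of eight endpoints, and it is likely to rest on few events: Protocol 3.2.4 describes placebo-arm mortality in recent trials as low. The SAP means to count deaths up to Day 368 in all randomized patients, on drug or off it. The protocol does not secure the data for that. A patient who leaves after an early last dose is censored when last known alive, and a later death reaches the sponsor only if the investigator happens to hear of it and reports it. Leaving is plausibly linked to worsening disease, so this censoring may be informative. Protocol 3.2.4 itself prefers all-cause mortality because censoring deaths judged unrelated can introduce bias.

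Transplant raises a related but smaller issue. The SAP tests its transplant censoring for PFS, which is ninth in the sequence, and for death or non-elective hospitalization, which is not in the sequence. It does not do so for the endpoint that holds the gate.

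**Working it through.** **1. The plan's own figures.** The stated power is for the primary endpoint: Φ(δ/(σ√(2/n)) − 1.96).
- Cohort A (n = 75 per arm, δ = 3.7, σ = 8): 3.7/1.306 = 2.83, giving 80.9% (80.3% with the t distribution).
- Cohort B (n = 165 per arm, δ = 2.5, σ = 8): 2.5/0.881 = 2.84, giving 81.0% (80.8%).

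Both agree with the stated figure of about 80%. No event count or power is stated for death.

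**2. Unobserved time.** Doses fall at Weeks 0, 4, ..., 48 (13 visits). Safety follow-up ends at last-dose week + 18.
- Last dose at Weeks 0, 4, ..., 32 (9 of 13 visits): ends at Weeks 18, 22, ..., 50. The gap to Week 52 is 34, 30, ..., 2 weeks (mean 18).
- Last dose at Week 36 or later: ends at Week 54 or later, so there is no gap if safety follow-up is completed.

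**3. Expected deaths.** The documents give no design death rate. As a range I take the one-year mortality for GAP Stages I, II and III in SAP Appendix 6 (5.6%, 16.2%, 39.2%), as if every control patient were in that stage, and assume HR 0.50 to 0.75. With 165 per arm, D = 165 × [p + 1 − (1 − p)^HR]:
- Stage I: 13.9 to 16.2 deaths
- Stage II: 40.7 to 47.2
- Stage III: 101.0 to 116.1

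**4. Deaths missed.** Let λ = −ln(1 − p), and let m be the leavers' hazard relative to other patients. For a leaver whose follow-up ends at week w, the chance of an unseen death by Week 52 is exp(−λm·w/52) − exp(−λm), averaged over the nine values of w. With N = 330 and HR 1:

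| Stage | λ | 10% exit, m = 1 | 20% exit, m = 2 |
|---|---|---|---|
| I | 0.0576 | 33 × 0.0191 = 0.6 | 66 × 0.0365 = 2.4 |
| II | 0.1767 | 33 × 0.0534 = 1.8 | 66 × 0.0934 = 6.2 |
| III | 0.4976 | 33 × 0.1178 = 3.9 | 66 × 0.1623 = 10.7 |

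That is 3-11% of all deaths.

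**5. Effect on the decision.** Simulation: 165 per arm, exponential times, unstratified log-rank test (the SAP's test is stratified), gate open if z < −1.96, exit equally likely in both arms. The decision with these exits differs from that with complete follow-up in 2-8% (Stage I), 3-11% (Stage II) and 2-9% (Stage III) of trials. Repeat runs put the upper end near 12%.

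For scale, take z = (b − a)/√(a + b). A split of 4 v 12 deaths gives z = 8/4 = 2.00, p = 0.046. If one placebo death goes unrecorded, 4 v 11 gives z = 7/√15 = 1.81, p = 0.071. Any test near its threshold behaves this way; the simulation shows how often it matters.

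**6. Transplant wording.** Take a patient transplanted at Week 20 who dies at Week 40. The sentence naming the death endpoint makes this an event. The transplant sentence censors at Week 20. With transplant assumed at 1-3% per year (no rate is given), the two readings give different decisions in about 0.3-4% of simulated trials.

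**The case against.** **Coverage is better than a quick reading suggests.** A reader might infer that nobody who leaves early is followed to Week 52. The documents do not support that. Patients who stop drug but stay in the study are covered, and so are leavers last dosed at Week 36 or later who complete safety follow-up. The gap concerns leavers last dosed at Week 32 or earlier and patients who withdraw consent.

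**Later reporting is not limited to related events.** Protocol 5.6 limits notification to serious events believed related to study drug. Protocol 5.3.1 asks for any serious event the investigator learns of once the study has ended. The two differ, but both depend on chance knowledge.

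**The transplant rule leans one way.** The SAP sentence applies to any patient, and Protocol 6.4.2 places the same sentence in the paragraph covering all time-to-event endpoints. Both favour censoring. This is a drafting conflict, not an open question of substance. It survives because SAP Section 1 says the SAP supersedes the protocol, and the SAP's own rule for death omits transplant.

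**Transplant as an event is a different endpoint.** Comparing death with death-or-transplant in simulation gives discordant decisions in 5-18% of Stage I trials. Across the Stage I scenarios, 13-59% of gates opened under censoring would not open with transplant as an event. A reader might take these as changes to the gate. They are not. No reading of the SAP counts transplant as an event in the death test, a sensitivity analysis cannot open or close the gate, and the shift goes both ways.

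**The inputs are soft.** Exit rates, transplant rates and death rates are all assumed, and Stage III sits poorly with the low mortality described in Protocol 3.2.4. The assumed 10-20% counts only exits after last doses at Weeks 0 to 32. If exits were even over the 13 visits, that would imply 10 × 13/9 = 14% to 20 × 13/9 = 29% leaving overall. The death test is also reached only if the primary succeeds. All of this stands and limits the size, not the existence, of the gap.

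**Conclusion.** The point holds, as something to consider. The test that gates eight endpoints counts deaths to Day 368, yet some early leavers are out of sight for 2 to 34 weeks before Week 52 with no planned vital-status check. Under the stated assumptions about 0.6 to 10.7 deaths are missed, and the decision differs from complete follow-up in about 2-12% of simulated trials. Stages I and II, the more plausible range, give 0.6 to 6.2 deaths. Because exit was simulated equally in both arms, these figures do not measure the bias if exit differs by arm. The transplant wording is secondary, with an effect of about 0.3-4%. The missing transplant analysis for death is an omission in an otherwise sensible set. Testing death first is a legitimate clinical priority and is not questioned.

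**What to change.** Before Cohort B is unblinded, keep the testing order and alpha, and:

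- **(a)** Where consent has not been withdrawn, ask sites for alive/dead status at Week 52 (Day 368) for patients who left early. State in SAP 4.4.3 that deaths found this way count in the death test, and report the number with unknown status by arm.
- **(b)** Add all-cause death to the transplant-as-event sensitivity analysis already planned for two other endpoints.
- **(c)** State in SAP 4.4.3 which censoring sentence governs a death after transplant.

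A tipping-point analysis on the unknowns would be useful but is optional.

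The cost is one site query, one extra run and a few SAP sentences. The query may need a short protocol clarification with the approvals described in Protocol 9.5. It cannot recover status for patients who withdrew consent. Sample size and visits do not change.
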